A Randomized, Controlled Trial to Determine the Efficacy of Active Topical Nail Solution versus Placebo Nail Solution for the Treatment of Pedal Onychomycosis

Funding Sponsor:	Marlinz Pharma [name] [contact]
Study Product:	Topical antifungal solution (Tolcylen™)
Protocol Number:	AFMC16
IND Number:	Not applicable
Date:	01/07/2019
Administrative Change:	12/11/2022, 02/20/2023

List of Abbreviations

AACFAS — Associate American College of Foot and Ankle Surgeons AE — adverse event

AE/SAE — adverse event/serious adverse event

AFMC — Ankle and Foot Medical Centers of the Delaware Valley

CITI — Collaborative Institutional Training Initiative (CITI Program)

COID — conflict of interest disclosure

COPD — chronic obstructive pulmonary disease

- CRF case report form
- DPM Doctor of Podiatric Medicine
- DSM data safety monitor

DSO — distal subungual onychomycosis

DTM — Dermatophyte Test Medium

EC/IRB — ethics committee/institutional review board

FACFAS — Fellow of the American College of Foot and Ankle Surgeons

FDA — Food and Drug Administration

HIPAA — Health Insurance Portability and Accountability Act of 1996

IRB — institutional review board

KOH — potassium hydroxide

MSCE — Master of Science in Clinical Epidemiology

OnyCOE-t[™] — Nail Specific Medical Outcomes Study

PAS — periodic acid-Schiff

QOL — quality of life

SAE — serious adverse event

VNPIS — visible nail plate involvement score

Study Summary

Title	A Randomized, Controlled Trial to Determine the Efficacy of Active Topical Nail Solution versus Placebo Nail Solution for the Treatment of Pedal Onychomycosis
Short Title	Topical Active Nail Solution versus Placebo
Protocol Number	AFMC16
Phase	This study is designed to compare the effects of active topical nail solution versus placebo nail solution in participants with pedal distal subungual onychomycosis (DSO).

CONFIDENTIAL

1	
Methodology	This is an interventional study comparing active topical nail solution versus placebo nail solution for the treatment of toenail fungal infection. All clinical and mycological examinations will be performed by blinded assessors; and baseline and post-treatment mycological and quality of life measurements will be analyzed in a single-subject paired fashion.
Study Duration	It is estimated that the duration of time necessary for the completion of this protocol (time from the start of screening to the last participant processed and finishing the study) will be 19 months.

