Number of Participants	Analyzing for the dichotomous outcome, either cured or not cured, using Fisher's exact test for independent groups (active topical nails solution alone versus placebo nail solution), in a prospective randomized fashion, expressing the alternative hypothesis as two proportions, at $\alpha = 0.05$, and $\beta = 0.80$, with the event rate in controls estimated to be 0.01 and the event rate in cases estimated to be 0.3, and using a 1:1 ratio of cases to controls, 29 participants will be needed in each treatment group in order to identify a statistically significant difference, should one exist. In anticipation of dropouts, limited site enrollment, and center effects and multiple center effects (≥6 clinical sites), an additional 20% will be added in an effort to ensure statistical power. Therefore, a minimum of 70 participants will be enrolled and randomized, subject to the data safety monitor's surveillance and recommendation.
Diagnosis and Main Inclusion Criteria	The main clinical disease under evaluation is toe onychomycosis. Participants will be males and non-pregnant females 18 years of age or older that have been diagnosed with distal subungual onychomycosis (DSO) involving at least one toenail. Diagnosis of this condition is to be made on the basis of history, physical examination, and a mycological inspection that includes a tissue examination for fungal hyphae (PAS stain). Evidence of fungal hyphae will be considered a positive confirmation of the diagnosis of toenail onychomycosis.
Study Product and Regimen	All participants will be randomized to either the active topical nail solution group, antifungal solution treatment, or to the placebo nail solution group. The topical antifungal medication under investigation is Tolcylen [™] . It will be provided by Marlinz Pharma, Houston, TX, the study funding Sponsor. The topical therapy will be applied in accordance with the existing FDA-approved method for use of this cosmetic agent.
Duration of administration	Administration of the interventions, active and placebo, will continue for no longer than nine (9) months. Administration of the topical agent may stop sooner if clinical and mycological evidence of cures are identified prior to nine (9) months.

CONFIDENTIAL

ponson marine i narina	

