Topical antifungals are generally recommended for the treatment of distal and lateral subungual onychomycosis with less than 50% of the visible nail plate surface area without matrix involvement, < 2-mm nail plate thickness, and ≤ 4 nails involved (39,40). FDA-approved topical agents that have shown efficacy for antifungal use include ciclopirox nail lacquer, efinaconazole, and tavaborole. According to the package insert for ciclopirox 8% nail lacquer, a complete cure was observed in 5.5% and 8.5% of cases, and the mycologic cure was 29% and 36% (41). Efinaconazole 10% solution had 17.8% and 15.2% complete cure incidences and 55.2% and 53.4% incidences of mycological cure; and tavaborole displayed 6.5% and 9.1% incidences of complete cure rate and 31.1% and 35.9% incidences of mycological cure (41-43). Interestingly, confirmatory mycology testing before treatment in not cost effective with terbinafine whereas it is with efinaconazole (9). Topical therapy can be relatively expensive, with average monthly supply costs of \$76.43 for ciclopirox, \$687.54 for efinaconazole, and \$1885.75 for tavaborole (44-46).

The Tolcylen[™] antifungal solution consists of tolnaftate as an active ingredient and undecylenic acid, lactic acid, propylene glycol and urea as delivery system ingredients. The patented low surface tension Tolcylen[™] Solution is the first product of its kind to combine FDA-approved antifungal medication with nail renewal, cosmetic and penetration enhancing ingredients. Tolnaftate, a thiocarbamate antifungal, blocks ergosterol biosynthesis, thus inhibiting fungal membrane formation (47). Tolnaftate has been used for superficial mycotic infection, such as tinea pedis due to Trichophyton rubrum, Trichophyton mentagrophytes, and Epidermophyton floccosum (48, 49). The delivery system ingredients in Tolcylen[™] also have antifungal properties, and they convey a cosmetic effect in that they improve nail appearance. In a multicenter, randomized, double-blind, placebo-controlled trial, a statistically significantly greater incidence of mycological cure was observed with a topical preparation of urea, propylene glycol and lactic acid compared to placebo; specifically, 27.2% vs. 10.4% placebo for ≤ 50% nail involvement, and 19.1% vs 7.0% placebo for 51-75% nail involvement, after 26 weeks of treatment for distal and lateral

CONFIDENTIAL

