The recruitment and screening period for potential participants will be 12 months (in order to identify 70 eligible participants) following the decision to initiate the protocol. It is expected that 70 participants will be informed and consented, and enrolled in the study, by approximately 12 months. Treatment for each participant will be carried out for a total of 9 months, or less if there is evidence of clinical

CONFIDENTIAL

and mycological cure prior to that time. The 9-month follow up visit will serve as the primary efficacy endpoint, in keeping with the usual expected minimum 7 to 9 -month duration of time expected for a full replacement of the visible nail plate in a typical adult human. Thereafter, a 3-month period will be allotted for completion of mycological testing and data collection. An additional 3 months will be allotted for completion of the analyses and 3 more months to write the report describing the study and submission of the manuscript for consideration for publication in a refereed journal. It is, therefore, estimated that the duration of time necessary for the completion of this protocol, data analysis, and preparation of the final report, will be approximately 35 months.

Study Centers

This study will be carried out at multiple clinical offices, under the guidance of different CITI-trained investigators, including:

- [name], DPM; Ankle & Foot Associates, [contact] (cell) Contact: Self; [contact], [name]. Site A
- [name], DPM; St Cloud Foot & Ankle; [contact] (cell) Contact: self; [contact] [name]. Site B
- [name], DPM; National Foot and Ankle, [contact] (cell) Contact: Self; [contact], [name]. Site C
- 4. [name], DPM; Family Foot Care, [contact] (cell) Contact: Self; [contact], [name]. Site D
- [name], DPM (the Principal Investigator); Foot & Ankle Specialists of Nevada, [contact] (cell) Contact: Self; [contact], [name]. Site E
- [name], DPM; A Step Ahead Foot and Ankle, [contact] (cell) Contact: Self; [contact], [name]. Site F
- [name], DPM, [name], DPM; The Division of Podiatry at The GW Medical Faculty Associates, [contact]) Contact: Office; [name]. Site G.

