The clinical disease under evaluation is pedal onychomycosis. Onychomycosis will be confirmed if fungal hyphae are observed on periodic acid-Schiff (PAS) stain examination of nail plate/bed tissue fragments. The fungal cell wall is composed of layers of chitin, glucan mannoproteins, and glycosylphosphatidylinositol, and the periodic acid-Schiff reaction colors these polysaccharides in the cell walls of fungi magenta. PAS staining of nail clippings is more sensitive than potassium hydroxide (KOH) and fungal culture for the diagnosis of onychomycosis (56). The PAS stain examination will be conducted by a certified microbiology laboratory of the site investigator's choice (their usual and customary practice) or an independent lab that has contracted with the sponsor to conduct the PAS test in support of the investigation. Each site investigator, or the contracted microbiology lab, will forward the results of the PAS tests for each participant. The payment for the baseline PAS stain will be handled by the patient's insurance, in the usual and customary fashion, since this is the typical requirement for standard treatment of mycotic toenails. Once again, anyone randomized to placebo nail solution will receive the active topical nail solution, Tolcylen[™], at the end of the treatment as described elsewhere in this protocol, if the participant desires. The PAS stain examination will be repeated at the termination of the intervention period, at either 3, 7 or 9 months after initiation of the intervention, and will be collected for the purposes of the investigation. As such, PAS assessments after the baseline test are not necessarily part of the clinician's usual and customary practice, since standard therapy usually does not entail a second mycology assessment if therapy has been successful. If, however, nail dystrophy persists, then a follow up PAS stain would be considered a reasonable component of standard therapy. To be fair to our participants, the cost of this final PAS assessment will be covered by the study sponsor. We will also randomly allocate a number of participants to either the active or placebo topical solution even if they do not have a PAS stain positive for fungal elements at baseline, in an effort to ascertain the influence that the active solution might have on non-mycotic dystrophic toenails. The investigation will not be powered a priori to see a statistically significant difference in this secondary analysis.

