It should be noted that the method of supply and application of both the placebo and the active topical nail solution is consistent with the standard method of use approved by the FDA monograph for use of an over-the-counter topical cosmetic agent, in accordance with the existing FDA monograph approved method for the treatment of dystrophic nails (see Tolcylen[™] label, Attachment 1). Participants in each group will be verbally instructed in the proper method of application of the topical solution and will also receive written instructions describing the study regimen and application technique (Attachment 2).

Upon arrival to the clinic for follow-up evaluation and care, the study participant will meet with a blinded investigator in the treatment room. The blinded investigator will review the study protocol and discuss any questions that the participant may have. The blinded investigator will inspect the participant's affected toes and procure the required information (clinical and photographic data) as delineated in this protocol.

Duration of Administration

For participants in both groups, maintenance of topical application of the assigned solution on the mycotic toenail/s will continue for a period of up to 9 (nine) months, for the purposes of the study. This duration of application is based

CONFIDENTIAL

on an average adult nail growth rate of 9 months for emergence from the proximal nail fold to the distal margin of the nail bed. Follow-up inspections will take place at 3, 7, and 9 months, following randomization and initiation of the treatment process. If participant shows clinical and mycological clearance prior to 9 months follow up, the participant may discontinue application of the topical nail solution if desired, in keeping with general clinical practice. The primary efficacy endpoint will occur at the minimum duration of 7-9 months, in keeping with the aforementioned and subsequently reviewed, proposed study timeline.

Timeline

The general design of this study is that of a randomized, controlled trial, wherein the intervention arms of the study consist of the application of either placebo or active topical nail solution, to be performed on volunteer human participants. The proposed study timeline is denoted in Table 2 and Fig. 1, below.

Milestone	Months
Screening visit and enrollment	12
3-month follow up visit	15
7-month follow up visit	18
9-mont follow up visit	21
Data analysis	27
Submit for publication	30

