In the event that a participant withdraws from the study prior to the termination of the designated follow-up period, every attempt will be made to inquire as to the rationale that the participant used in deciding to withdraw. Moreover, permission will be sought to collect at least survival (time to event) data. In light of the importance of complete follow-up, in relation to the integrity of the research study, the following steps will be taken prior to concluding that a participant is definitely lost to follow-up:

- 1. Three separate telephone calls on three separate days, each to the participant's home and place of work.
- 2. A letter sent to the participant's residence via certified mail, asking the individual to contact the study center to discuss their progress and participation in the study.
- 3. A telephone call to the participant's next of kin, to inquire as to the participant's whereabouts and participation in the study.

Statistical Plan

Power and Sample Size Determination

CONFIDENTIAL

Analyzing for the dichotomous outcome, either cured or not cured, using Fisher's exact test for independent groups (active topical nail solution and placebo), in a prospective randomized fashion, expressing the alternative hypothesis as two proportions, at $\alpha = 0.05$, and $\beta = 0.08$, with the event rate in controls as 0.01 and the that in cases as 0.3, and using a 1:1 ratio of cases to controls, we will need 29 participants in each treatment group, or 58 participants overall, to be able to detect a statistically significant difference between the treatment arms. In anticipation of dropouts, limited site enrollment and center effects and multiple center effects (6 clinical sites), an additional 20% will be added in an effort to ensure statistical power. Therefore, a total of 70 participants will be enrolled and randomized, subject to the data safety monitor's surveillance and recommendation.

Statistical Methods

The primary endpoint in this study is the mycological presence or absence of fungal hyphae in fragments of the index toenail as viewed on the microscopic PAS stain, following the application of active topical nail solution, or placebo nail solution, to participant's mycotic toenails.

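### The primary PAS endpoint has no single time point: month 9, 7–9 months, or whichever of months 3, 7 or 9 treatment ends, so early stoppers need have no month-9 specimen

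*Protocol*

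**What the plan says.** All references are to the protocol.

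- **Statistical Methods** defines the outcome but not its time: "The primary endpoint in this study is the mycological presence or absence of fungal hyphae in fragments of the index toenail".
- **Study Duration** (main text): "The 9-month follow up visit will serve as the primary efficacy endpoint".
- **Duration of Administration**: "The primary efficacy endpoint will occur at the minimum duration of 7-9 months".
- **Diagnosis of Primary Outcome**: the PAS is "repeated at the termination of the intervention period, at either 3, 7 or 9 months after initiation of the intervention". The same section treats this as one final PAS, paid for by the sponsor.
- **Early ending of application.** The Study Summary says: "Administration of the topical agent may stop sooner if clinical and mycological evidence of cures are identified prior to nine (9) months". Duration of Administration makes it optional: after clearance "the participant may discontinue application of the topical nail solution if desired".
- **Follow-up visits** fall at months 3, 7 and 9. Study Product, Dose, Route and Regimen names clinical and photographic data for them and does not mention a PAS.
- **PAS accuracy.** The Review of the Literature gives a sensitivity of 61% to 98%.

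**The concern.** The time of the primary measurement decides when a site takes the specimen. A site that follows Diagnosis of Primary Outcome takes the deciding PAS when application ends. A site that follows Study Duration takes it at month 9. For a participant who clears early, these are different specimens, months apart.

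Three things are at stake:

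1. The endpoint stated for month 9 is not measured in those who stop early.
2. The measurement time depends on the outcome, because a good early result brings the deciding reading forward. A nail that is negative at month 3 or 7 and positive again by month 9 counts as cured.
3. If an early PAS is positive and application continues, nothing says which PAS counts. With an imperfect test, counting any negative would give some infected nails more than one chance to be called cured.

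**Working it through.** **Step 1. Is there one time point?**

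| Section | Time of the primary result |
|---|---|
| Statistical Methods | none given |
| Study Duration | 9-month visit |
| Duration of Administration | 7–9 months |
| Diagnosis of Primary Outcome | end of intervention: month 3, 7 or 9 |

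The three times agree only for a participant treated to month 9. The endpoint definition does not choose among them.

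**Step 2. What happens to a participant who clears early?** Ending before month 9 needs clinical and mycological clearance. Under Diagnosis of Primary Outcome the PAS belongs to that moment, and no section requires another at month 9. The text is also circular: the PAS is taken at termination, yet early termination needs a negative PAS. If the early PAS is positive and application continues, another PAS is due at the end, and no rule ranks the two. For a participant later lost to follow-up, the last-observation rule in Participant Population(s) for Analysis would carry an early negative forward as the later result.

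**Step 3. How large could a retesting effect be?** This step is conditional. For a nail that is still infected, with sensitivity s, up to k tests, independent errors and stopping at the first negative:

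chance of a false negative = 1 − s^k

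| s | 1 test | 2 tests | 3 tests |
|---|---|---|---|
| 0.98 | 2.0% | 4.0% | 5.9% |
| 0.90 | 10% | 19% | 27% |
| 0.80 | 20% | 36% | 49% |
| 0.61 | 39% | 63% | 77% |

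The values 0.98 and 0.61 are the ends of the protocol's range; 0.90 and 0.80 are intermediate values chosen here. Three tests is the upper bound, for someone tested at every visit.

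Suppose there is no mycological effect, a share q of an arm has up to three tests and the rest have one. The false-cure rate is q(1 − s³) + (1 − q)(1 − s). Take q = 40% on active and 5% on placebo (assumed):

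- s = 0.90: 0.4 × 0.271 + 0.6 × 0.10 = 16.8%, against 0.05 × 0.271 + 0.95 × 0.10 = 10.9%.
- s = 0.80: 0.4 × 0.488 + 0.6 × 0.20 = 31.5%, against 0.05 × 0.488 + 0.95 × 0.20 = 21.4%.

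The chance of a false win for active follows by exact enumeration, with 35 per arm (70/2), two-sided Fisher's exact test at 0.05 and q = 5% on placebo:

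| q on active | s = 0.98 | s = 0.90 | s = 0.80 | s = 0.61 |
|---|---|---|---|---|
| one test for all, both arms | 0.0% | 0.7% | 1.3% | 1.4% |
| 10% | under 0.1% | 1.1% | 1.8% | 2.0% |
| 20% | under 0.1% | 2.0% | 3.5% | 4.0% |
| 40% | under 0.1% | 5.4% | 10.2% | 12.8% |

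The nominal level is 2.5% per side. Exchanging the two shares would give placebo the same advantage.

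**Step 4. Does the fix alter the sample size?** No. The planned 29 per group (rates 0.01 and 0.30) has 84.3% power by exact two-sided Fisher enumeration, and that calculation does not depend on the time of the PAS.

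**The case against.** The strongest reply is that only the wording conflicts and that the bias story goes beyond the text. Much of this stands.

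- **Number of tests.** A reader might infer that better-looking nails get up to three PAS attempts and others one. The protocol describes a single final PAS. Retesting follows only if an early PAS is positive and application goes on, which is inferred.
- **Direction.** A reader might also infer that the extra attempts favour the active arm, since the delivery ingredients are said to have antifungal properties and "they convey a cosmetic effect in that they improve nail appearance". But the only sentence linking a follow-up PAS to appearance concerns nails whose dystrophy persists, which points the other way. Participation may also end early through withdrawal or worsening infection. The direction is not established.
- **Size.** A 40% share is close to a worst case. Clinical cure is a VNPIS fall of at least 60%. With a minimum score of 7, this is possible only from a baseline of 7/0.4 = 17.5 or more, and the protocol expects full nail replacement to take about 9 months.
- **Calendar.** The summary's "time from the start of screening to the last participant processed and finishing the study) will be 19 months" equals 12 + 7, and a reader might take that as a sign of an intended 7-month endpoint. It is weak evidence. Table 2 puts the last visit at month 21 (12 + 9) but the 7-month visit at month 18 (12 + 7 = 19). The components in Study Duration sum to 12 + 9 + 3 + 3 + 3 = 30, against a stated 35. The calendar is unreliable throughout.
- **Relapse.** All participants are to be followed to the end and the VNPIS is repeated at each visit, so clinical relapse can be seen. Only mycological relapse is missed.

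None of this removes the three conflicting times or supplies the month-9 specimen. Nor can the matter be left to an analysis plan, since it governs what sites collect. Visit forms calling for a PAS at every visit (they are not shown) would still leave open which result is primary.

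**Conclusion.** The point holds as a timing defect in the primary endpoint and should be corrected. The conflict is in the protocol's own words and needs no assumption. Its direct consequence is that participants who stop early may have a primary result from month 3 or 7, with the stated 9-month outcome and mycological relapse by then unmeasured. How many this affects cannot be derived from the protocol.

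The retesting bias is a conditional risk, not a finding. It requires that retesting occurs, that it is more common in one arm, that errors are roughly independent and that any negative counts. Under the assumed shares shown, the false-win chance for active runs from under 0.1% at 98% sensitivity to 12.8% at 61% with a 40% share. It is small where few are retested or sensitivity is near 98%.

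**What to change.** - **Statistical Methods:** define the primary endpoint as the PAS result on an index-nail specimen taken at the scheduled month-9 visit, for every randomised participant who was PAS-positive at baseline, whether or not application ended earlier. Record any month-3 or month-7 PAS, but do not count it as the primary result.
- **Alignment:** bring Study Duration, Diagnosis of Primary Outcome and Duration of Administration into line, and correct the duration in the Study Summary.
- **Population:** square the PAS-positive restriction with Participant Population(s) for Analysis, which assigns the primary analysis to all randomised, although some PAS-negative participants are also to be randomised. Say there how a missing month-9 PAS is handled, so that carrying forward does not bring an early PAS back as the primary result.
- **Early ending of application:** the clinicians must reconcile the statements in the Study Summary, Study Duration, Diagnosis of Primary Outcome and Duration of Administration. No stopping rule is proposed here.

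The cost is wording, plus one further PAS for each participant who ended application early. The month-9 visit is already scheduled, and the planned 29 per group is unchanged.

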Table 1 Topical solution tube site-participant designation*

CONFIDENTIAL

A4	B4	C4	D4	E4	F4	G4	H4	J4
A5	B5	C5	D5	E5	F5	G5	H5	J5
A6	B6	C6	D6	E6	F6	G6	H6	J6
A7	B7	C7	D7	E7	F7	G7	H7	J7
A8	B8	C8	D8	E8	F8	G8	H8	J8
A9	B9	С9	D9	E9	F9	G9	H9	J9
A10	B10	C10	D10	E10	F10	G10	H10	J10
An	Bn	Cn	Dn	En	Fn	Gn	Hn	Jn

*This designation correlates with the randomization schedule and enables the principal investigator to keep track of active and placebo distribution and use.

A study coinvestigator, not participating at a study site, and not tasked with data analyses, will maintain the random allocation code, which will contain this same information as well as the randomly allocated topical solution, denoted as either the placebo nail solution or the active topical nail solution.

Inclusion and Exclusion Criteria

Inclusion criteria for participation in this study include:

- 1. Male or female participants aged 18 years or older;
- 2. If female is of childbearing potential, she must not be pregnant at the time of enrollment and she must be using an accepted form of birth control during the study treatment period (acceptable forms include: postmenopausal, surgical sterility, complete abstinence, sterilized sexual partner, tubal occlusion, copper-T intrauterine device, levonorgestrelreleasing intrauterine device, medroxyprogesterone injections, etonogestrel implants, combined pills, norelgestromin/ethinly estradiol transdermal system, intravaginal device, or Cerazette pill; and for males the use of a condom with spermicide or surgical sterility);
- 3. Participant has a diagnosis of onychomycosis diagnosed by means of history, physical examination, and positive (evidence of fungal hyphae) mycological tissue examination by periodic acid-Schiff (PAS) staining;
- 4. At least one toe nail with distal subungual involvement, localized to any toe, with at least 10% involvement and including up to 100% involvement of the visible nail plate, any nail plate thickness, with the index nail being the most involved per inspection by the on-site investigator and agreed upon by the designated co-investigator study doctor ([name], DPM), who will inspect specific clinical photographs of the involved nail/s (the photographs will be obtained at each study site using a specified method, as demonstrated to site investigators, so that the clinical features are appropriately demonstrated);

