Secondary endpoints are changes in the participants' toenail-related quality of life, as measured using the OnyCOE-t[™] quality of life questionnaire (56,57), and changes in the appearance of the index toenail as measured using the visible nail plate involvement score. Additional demographic exposure variables will also be collected and analyzed in order to describe the participants in the study. Specifically, the participant's age, sex, body mass index (BMI), comorbidities and medications, as well as the number of mycotic toe nails, the duration of onychomycosis based on the participant's history, the presence of pedal digital deformity (hammer toe, claw toe, if present), and any local or systemic complication/s that may arise during the course of the investigation.

All participants will be followed to the endpoint of the study, in accordance with the proposed timeline. The data will be considered based on type and distribution. An intention-to-treat analysis will be used, and it will entail descriptive statistical methods, including mean and standard deviation, or median and quartile, to describe demographic variables; as well as tests of the null hypothesis that will include 2-sample Student's *t*-tests, or Wilcoxon rank sum tests, for differences between the two study groups both before and after intervention, and paired *t*-tests, or Wilcoxon signed ranks tests, for comparison of pre- and post-treatment results in single participants, for continuous data, depending on the distribution of the data. The statistician will be blind to treatment allocation, which will be denoted as "A" or "B" until the results are computed, after which time the precise nature of the allocation will be revealed.

CONFIDENTIAL

Participant Population(s) for Analysis

The specific population to be included in this intention-to-treat analysis will be the all-randomized population (any participant randomized into the study, regardless of whether they underwent topical application of active topical nail solution or the placebo). This population will be subjected to primary and secondary endpoint analyses. For any participant lost to follow, their last observation will be carried forward for the subsequent evaluations in accordance with the study timeline.

Safety and Adverse Events

Definitions

Adverse Event

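### Applied as written, the all-randomised primary population includes participants with no fungus on PAS at baseline, who would nearly all score as successes in both arms and dilute the treatment difference

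*Protocol*

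**What the plan says.** Four places in the protocol bear on this.

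- **Inclusion and Exclusion Criteria, inclusion 3.** The diagnosis must rest on history, examination and a "positive (evidence of fungal hyphae) mycological tissue examination by periodic acid-Schiff (PAS) staining". The Study Population section and the synopsis define the population in the same way.
- **Diagnosis of Primary Outcome.** Some participants will nevertheless be allocated to "either the active or placebo topical solution even if they do not have a PAS stain positive for fungal elements at baseline". The aim is to see what the active solution does for dystrophic nails that are not mycotic. The section calls this a secondary analysis and says it is not powered. It gives no number.
- **Statistical Methods.** The primary endpoint is whether hyphae are present or absent on PAS of the index toenail after treatment. The sentence refers to participants' mycotic toenails but sets no explicit requirement of a positive baseline stain.
- **Participant Population(s) for Analysis.** The population is "any participant randomized into the study, regardless of whether they underwent topical application of active topical nail solution or the placebo". The section then says: "This population will be subjected to primary and secondary endpoint analyses". For anyone lost to follow-up, the last observation is carried forward.

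No section states how many baseline-negative participants there may be, whether they count towards the 70, or that they are left out of the primary analysis.

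**The concern.** A nail without hyphae at baseline that is still without hyphae at the end meets the favourable outcome with no treatment effect. If that participant drops out before the final stain, carrying the last observation forward records the baseline negative as a success. Because allocation is random, such participants raise the success rate in both arms and shrink the difference between them. The 1% placebo rate behind the sample size is plausible only if everyone analysed starts with a positive stain. If these participants also count towards the 70, they take places from people who could show a cure. The primary result would then describe a mixture of confirmed and unconfirmed disease, whereas the research question concerns onychomycosis.

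**Working it through.** **Inputs.** The Power and Sample Size Determination section uses this test: "Analyzing for the dichotomous outcome, either cured or not cured, using Fisher's exact test for independent groups". It sets α at 0.05 "with the event rate in controls as 0.01 and the that in cases as 0.3", with 29 per arm, 58 in total, and 70 after adding 20%. Sidedness is not stated; two-sided is assumed. The synopsis gives β as 0.80, evidently meaning power, and the Statistical Plan gives β as 0.08.

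**Reproducing the plan's figure.** With p̄ = (0.01 + 0.30)/2 = 0.155, the usual formula is

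n = [1.96·√(2 × 0.155 × 0.845) + 0.842·√(0.01 × 0.99 + 0.30 × 0.70)]² / 0.29² ≈ 23.2, so 24 per arm.

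The continuity correction raises this to 30, against 29 stated. Exact two-sided Fisher power at 29 per arm is 84.3%. The stated size therefore fits 80% power. It does not fit 92% (a literal β of 0.08), which needs 33 per arm without the correction and 40 with it. So 80% is taken as the planned level. Then 58 × 1.2 = 69.6, rounded to 70, or 35 per arm.

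**Effect of a baseline-negative share f.** If all such participants stay negative, the expected success rate in an arm is p = (1 − f)·p₀ + f, with p₀ = 0.01 or 0.30. Exact Fisher power at 35 per arm:

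| f | Placebo | Active | Difference (points) | Power |
|---|---|---|---|---|
| 0 | 1.0% | 30.0% | 29.0 | 93.5% |
| 10% | 0.9 × 1 + 10 = 10.9% | 0.9 × 30 + 10 = 37.0% | 26.1 | 65.6% |
| 20% | 0.8 × 1 + 20 = 20.8% | 0.8 × 30 + 20 = 44.0% | 23.2 | 46.2% |

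If only 90% of them test negative at the end, power is 67.3% and 47.3% for the last two rows, so the result hardly depends on that assumption.

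**Effect of a fixed number m per arm.** Here exactly m participants per arm are certain successes and the rest respond at 1% or 30%. Power is summed over all tables with Fisher p ≤ 0.05.

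| m per arm | Inside the 70, all randomised analysed | On top of the 70, all analysed | Inside the 70, baseline-positive only |
|---|---|---|---|
| 0 | 93.5% | 93.5% | 93.5% |
| 2 | 83.9% | 87.7% | 91.2% |
| 3 | 73.9% | 82.3% | 89.8% |
| 4 | 67.0% | 79.1% | 88.2% |
| 7 | 43.0% | 67.7% | 81.9% |

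The two tables differ slightly at similar shares (43.0% here for m = 7, 46.2% above for f = 20%). The first lets the number of negatives vary by chance in each arm; the second fixes it and balances it. Neither allows for dropout.

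**The case against.** The strongest reply is that the protocol does not mean to count these people. The endpoint sentence speaks of mycotic toenails, the added group is described as non-mycotic, and its comparison is labelled secondary. A nail without fungus cannot be cured, and a 1% placebo rate fits only baseline-positive nails. The analysis plan, which is not at hand, might settle the matter. This stands as evidence of intent. A reader might infer that the protocol expressly rules baseline negatives to be cures; it does not, and that follows only from applying the population definition literally. Still, that definition is explicit and has no exception. Calling one comparison secondary does not remove its participants from another, and an analysis plan restricted to baseline positives would depart from the protocol's wording.

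A reader might also infer that power necessarily falls well below the planned 80%. The documents do not support that: neither the number nor the placement is given, and power stays above 80% with up to 2 per arm inside the 70 or 3 per arm on top.

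Nor is there systematic bias towards one arm. Random allocation protects the type I error, and chance imbalance in these participants is sampling variation that the test already allows for.

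Finally, some baseline negatives may be false negatives, since the literature review cites PAS sensitivity of 61% to 98%. Hence nearly all, not all, would score as successes.

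**Conclusion.** The point holds as a contradiction within the protocol, with a conditional cost. Eligibility requires a positive baseline PAS, another section waives it for an unstated number, and the population rule, read as written, brings those participants into the primary analysis. The consequence is dilution and loss of power. It is minor with 1 or 2 per arm (88.7% and 83.9% inside the 70) and serious from about 10% of participants upwards (about 66%, falling to about 46% at 20%). These figures are scenarios. They rest on the protocol's 30% v 1%, a two-sided Fisher test at 0.05, 35 per arm unless the negatives are added on top, no dropout, and baseline negatives remaining negative.

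**What to change.** Define the primary mycological population as all randomised participants with a positive baseline PAS, analysed in the arm to which they were allocated. Report baseline-negative participants only as a separate exploratory dystrophic-nail cohort, using the visible nail plate involvement score and OnyCOE-t. Reconcile inclusion 3, Diagnosis of Primary Outcome, Statistical Methods and Participant Population(s) for Analysis accordingly. Provided the baseline specimen is taken before allocation, selecting on its result keeps the randomised comparison intact.

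This is enough by itself and costs only wording, plus a smaller primary sample if the negatives are inside the 70. With 7 per arm removed, 28 per arm remain and power is 81.9%, against 43.0% if they are kept in.

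A separate allocation list is optional. So is not counting these participants towards the 70, but that could require extra recruits, visits, site payments and sponsor-funded final PAS tests.
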